5.3 Duration of Therapy

Subjects will be removed from study if one of the following occurs:

- Subjects who do not complete at least 50% of the planned medical therapy
- Intercurrent illness that prevents further administration of medical treatment,
- Unacceptable adverse event(s),
- Patient decides to withdraw from the study, or
- General or specific changes in the patient's condition render the patient unacceptable for further treatment in the judgment of the investigator.

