1.2 Secondary Objectives

- Quantify changes in strength, and body composition, before and following supplementation
- Determine feasibility of beetroot supplementation in head and neck cancer patients defined for each patient as the proportion of days successfully consumed supplement during treatment schedule
- Determine the toxicity of concentrated beetroot given in conjunction with radiation or chemo-radiation in SCCHN as measured by CTCAE v. 4.0
- Evaluate the trend in grade of mucositis during radiotherapy or chemoradiotherapy as measured weekly by CTCAE v 4.0
- Determine 1- and 2-year locoregional control rate and progression-free survival of subjects enrolled on this clinical trial.

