5.4 Duration of Follow Up

The response to treatment will be made by repeating clinical and radiological studies as per standard of care (at 6-12 weeks) and repeated during follow up as per NCCN guidelines. Patients will be followed until resolution of all grade 2 or greater toxicities.

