5.5 Criteria for Removal from Study

Patients will be removed from study when any of the criteria listed in Section 5.4 applies. The reason for study removal and the date the patient was removed must be documented in the Case Report Form.

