10.2 Calendar for Beetroot Supplementation Cohort

Timepoints	Baseline	Weekly during Concurrent Radiation and Cisplatin	Midpoint (After IMRT)	Endpoint (4-6 weeks following Midpoint testing)	Off-treatment	Off study
Studies:						
H&P ¹ VS	X	X	X	X	X	X
TOX	X	X	X	X		
Pregnancy Testing	X					
Muscle Strength and Endurance Testing	X		X	X		
Body Composition (DXA)	X		X	X		
Plasma/Salivary Nitrate/Nitrite	X		X	X		
QOL and Mucositis	X		X	X		
Diet	X		X			
Ct SCAN (body comp)	X		X	X		
Routine Cancer Imaging ²	X			X		X
Treatments:						
Beet Root (daily) ³	X	X	X	X		

1) Abbreviations: H&P=History and Physical examination; PS=ECOG performance status; VS=vital signs (blood pressure, temperature, pulse and respiratory rates, weight and height); TOX=toxicity assessment

2) Routine cancer imaging will be standard of care CT or MRI scans to document disease and response to therapy. These will be required pre-treatment, post-chemoradiation and at 1- and 2-year follow-up (+/- 6 weeks), as per standard of care.

3)Beet root will be self-administered each day (M-F in afternoon)

4)Toxicity will be followed for all patients until (endpoint) testing. Any beetroot related toxicity $>$ grade 2 will be followed until resolution to grade 1 or less.

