13.4.2 Evaluation of Outcomes

All patients included in the study will be assessed for treatment compliance, even if there are major protocol treatment deviations or if they are ineligible. All of the patients who met the eligibility criteria (with the possible exception of those who received no study medication) will be included in the intent to treat analysis for the primary completion endpoint as well as all secondary outcomes.

Due to concerns of potential non-compliance of taking all beet supplements over the course of primary treatment, a per protocol analysis will also be performed for all patients that consume at least 3 servings of the required beet supplements per week. Percentage of beet supplements taken will also be reported as part of this subgroup analysis.

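### Section 5.3 takes patients who fail treatment off the study, and nothing says their secondary outcome data are still collected

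*Combined protocol and SAP*

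**What the plan says.** Section 5.3 opens with "Subjects will be removed from study if one of the following occurs". Its first criterion is "Subjects who do not complete at least 50% of the planned medical therapy"; the others are intercurrent illness that prevents treatment, unacceptable adverse events, patient withdrawal, and a change in condition that the investigator judges unacceptable for further treatment.

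Section 5.4 sets response assessment at 6–12 weeks, "repeated during follow up as per NCCN guidelines", and adds "Patients will be followed until resolution of all grade 2 or greater toxicities". Section 5.5 states "Patients will be removed from study when any of the criteria listed in Section 5.4 applies" and requires the date of and reason for removal on the case report form. The criteria themselves are in 5.3, not 5.4.

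Against this stand three commitments:

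- Section 1.2: "Determine 1- and 2-year locoregional control rate and progression-free survival of subjects enrolled on this clinical trial".
- Section 10.2, footnote 2, on routine cancer imaging in the beetroot cohort: "These will be required pre-treatment, post-chemoradiation and at 1- and 2-year follow-up (+/- 6 weeks), as per standard of care". The same calendar marks the physical examination and cancer imaging in its Off study column.
- Section 13.4.2: eligible patients, possibly excepting those who took no study medication, "will be included in the intent to treat analysis for the primary completion endpoint as well as all secondary outcomes".

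Section 13.3 names repeated measures ANOVA and Kaplan-Meier curves. It gives no missing-data rule for the first and no censoring rule for the second.

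**The concern.** Most of the 5.3 criteria are outcomes that arise after enrolment and are closely tied to the primary endpoint. If meeting one ends data collection, the patients with missing secondary data are those who tolerated treatment worst. An intent-to-treat label cannot supply measurements that were never taken.

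The protocol's own background points to the likely direction. Section 2.1 says that failing to receive all planned chemotherapy affects survival and local control, and 2.3 links treatment compliance directly to clinical outcome. On that premise removed patients have the worse prognosis, so results from those who remain would look too good. The same applies to strength and fat-free mass: the central hypothesis in 2.5 is that the supplement works by limiting their loss, and the patients dropped are those most informative about it.

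At stake are the secondary estimates that a pilot hands on to the larger study mentioned in 13.2.

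**Working it through.** **The plan's own figures.** The only precision figures given are for the compliance rate (13.2): 90% half-widths of at most 27.75, 22.85 and 17.7 points for n = 10, 15 and 25. The largest half-width of the exact (Clopper-Pearson) 90% interval over all possible counts is 27.76, 22.81 and 17.67 points, so they reproduce. The plan gives no figure for LRC, PFS, strength or body composition, and no removal rate.

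**Timing of the tests.** Section 5.1.1.1 gives 30–35 fractions over 6–7 weeks, so half the course is reached at about week 3 to 3.5. Section 5.1.5 puts midpoint testing at week 7–8 from the start of IMRT and endpoint testing 4–6 weeks later, at about week 11–14. A patient removed before the halfway point leaves before both post-baseline tests. The 10.2 calendar lists strength, DXA and body-composition CT at baseline, midpoint and endpoint only, with nothing under Off-treatment or Off study.

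**Loss of precision.** If 2, 3 or 5 of the 25 beetroot patients have no data, the maximum exact 90% half-width for a binary outcome rises from 17.7 to 18.4, 18.9 or 19.8 points. This is minor.

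**Bounds without a prognosis assumption.** Take about 60% success among those observed and count the missing patients first as all failures, then as all successes:

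- 2 missing, 14/23 observed: 14/25 to 16/25 = 56–64%.
- 3 missing, 13/22 observed: 13/25 to 16/25 = 52–64%.
- 5 missing, 12/20 observed: 12/25 to 17/25 = 48–68%.

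**Possible bias in 2-year PFS.** All inputs here are assumptions: exponential times; 2-year PFS of 65% in retained patients; a fraction f of 8%, 12% or 20% (2, 3 or 5 of 25) removed and censored at month 1; hazard ratio HR for removed against retained patients.

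- Monthly hazard in retained patients: λ = −ln(0.65)/24 = 0.01795.
- True rate in all enrolled: (1 − f) × 0.65 + f × 0.65^HR, with 0.65² = 0.4225 and 0.65⁴ = 0.1785.
- Expected Kaplan-Meier value: [(1 − f) × e^(−λ) + f × e^(−HR·λ)] × e^(−23λ).

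| HR | f | All enrolled (%) | Kaplan-Meier (%) | Overstatement (points) |
|---|---|---|---|---|
| 1 | any | 65.0 | 65.0 | 0 |
| 2 | 8% | 63.2 | 64.9 | 1.7 |
| 2 | 12% | 62.3 | 64.9 | 2.6 |
| 2 | 20% | 60.5 | 64.8 | 4.3 |
| 4 | 8% | 61.2 | 64.7 | 3.5 |
| 4 | 12% | 59.3 | 64.6 | 5.2 |
| 4 | 20% | 55.6 | 64.3 | 8.7 |

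Differences are taken before rounding. A simulation under the same assumptions agrees to within simulation error.

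**The case against.** The strongest reply is that 5.3 is a loosely worded off-treatment list. Its heading concerns duration of therapy, two of its items speak of further treatment, and much of the rest of the protocol assumes that disease follow-up goes on. Section 5.4 calls for guideline-based imaging, footnote 2 of 10.2 requires scans at 1 and 2 years, the calendar marks examination and imaging in the Off study column, and 11.2.4.3 asks that progression be documented after treatment stops for global deterioration. Section 13.4.2 excludes nobody for being removed. The affected outcomes are descriptive and exploratory, in a pilot not powered for comparison, and every bias figure above lies well inside the planned ±17.7 points.

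Much of this stands. A reader might infer from 5.4 that all follow-up ends once toxicity resolves. The text does not support that: the same section provides for continued imaging, and the toxicity sentence can be read as governing toxicity follow-up only. A reader might also take 5.5 to make toxicity resolution a removal criterion, but its pointer to 5.4 is a cross-reference slip.

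What does not fall away is the wording of 5.3 together with 5.5, which turns removal from the study into a recorded event with a date. The passages on continued follow-up concern disease status. None keeps strength, DXA or body-composition testing going after removal, and none says that footnote 2 overrides removal. Staff could follow either reading.

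**Conclusion.** The point holds as a contradiction to be reconciled. For strength and body composition, following 5.3 as written loses both post-baseline tests in patients removed early, contrary to 13.4.2. For LRC and PFS the loss is possible but not stated.

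The primary endpoint is safe: 13.4.2 assesses every patient for treatment compliance despite major deviations, and a patient who stops early counts as non-compliant.

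Under the stated assumptions PFS would be overstated by 0 points at a hazard ratio of 1, about 1.7–4.3 at 2 and about 3.5–8.7 at 4. Neither the removal rate nor the prognosis of removed patients is in the documents, and the calculation assumes that all their later disease information is lost. It is tempting to quote a larger fixed figure. For example, a 40-point gap in 2-year PFS with 3 to 6 of 25 removed gives 3 × 40/25 = 4.8 to 6 × 40/25 = 9.6 points. That range takes the gap for granted and hides the possibility of no bias, so it should not be cited as the size of the problem.

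The change should be made because it is cheap and protects the estimates carried forward; it does not threaten the trial's main result.

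**What to change.** Reconcile 5.3, 5.4, 5.5, footnote 2 of 10.2 and 13.4.2 so that stopping treatment and leaving data collection are separate events. The clinical stopping criteria themselves stay with the sponsor.

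- **5.3:** state that a patient who meets any criterion other than withdrawal of consent continues midpoint and endpoint testing if willing, and 1- and 2-year follow-up of disease and vital status.
- **5.4:** state that disease follow-up runs to 2 years, and that resolution of toxicity governs toxicity follow-up only.
- **5.5:** correct the reference to 5.3.
- **13.3:** a sentence on how LRC and PFS are censored, and how missing repeated measures are handled, would make any remaining loss visible.

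The cost is protocol wording and a few more follow-up contacts. The 1- and 2-year imaging is already described as standard of care in the beetroot calendar.

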5.4 Duration of Follow Up

The response to treatment will be made by repeating clinical and radiological studies as per standard of care (at 6-12 weeks) and repeated during follow up as per NCCN guidelines. Patients will be followed until resolution of all grade 2 or greater toxicities.

5.5 Criteria for Removal from Study

Patients will be removed from study when any of the criteria listed in Section 5.4 applies. The reason for study removal and the date the patient was removed must be documented in the Case Report Form.

6. DOSING DELAYS/DOSE MODIFICATIONS

The following dosing delays and dose modifications refers only to adverse events which are at least possibly related to beetroot juice. When grade 3 and 4 toxicities are encountered and are possibly, probably or definitely related to beetroot juice, please use the following dose reduction table.

Event	Management/Next Dose for Beet Root
≤ Grade 1	No change.
Grade 2	No change

Event	Management/Next Dose for Beet Root
Grade 3 or 4	Hold until recovery to grade 2 or less, then decrease to Monday-Wednesday-Friday dosing

Exceptions to this procedure include: any grade alopecia and grade 3 or 4 fatigue.

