5.1.3 Beetroot Administration

Study Supplements:

Subjects will be given 10 grams of concentrated organic beetroot crystals to mix with 120ml of water (BEETELITETM). Beetelite study supplement readily dissolve in water and may be given via gastrostomy tube or orally.

Daily Supplement Administration:

Subjects will begin daily supplementation following baseline measures (1-2 weeks before 7-week IMRT and for a minimum of 4 days) and will continue supplementation 4-6 weeks after treatment. Patients will be taught to self-administer their assigned study beverage by mouth and via PEG (as needed) by study staff during the baseline measurement period for the entirety of the trial. Patients requiring enteral support will be taught how to self-administer their assigned study beverage by a CRA or CRN. Compliance will be monitored by verbal assessment at clinic visits and by collection of written logs. Written instructions (Appendices E and F) for proper mixing of study beverage powders with water will be provided to both study volunteers and MCC staff involved in supplement administration and supervision. MCC staff will supervise the initial self-administration to ensure uniformity of ingestion. Subjects will be required to record the supplement intake in a dietary log which will be reviewed frequently at clinic visits.

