- CRNs serving as study personnel may offer observation or administration assistance if patient requests this and may document supplement compliance.
- Patients will be instructed to make up any missed doses by taking up to 1 additional dose per day on the weekend days. Patients will receive 5 doses per week (for M-F) and will be instructed to never exceed 1 dose per day.

4-6 weeks post-IMRT (discharge period):

- After completion of IMRT the participant will be instructed to continue daily (M-F) self-administration (PO or PEG) until completion of endpoint measures.
- For patients requiring supplement administration assistance at discharge, a family member or caregiver will be identified and taught to provide assistance.
- On the day of discharge and during scheduled follow-up visits, the CRA will distribute the pre-measured supplement packets needed for daily administration.
- Participants will continue to follow the supplement mixing protocol and be reminded to consume their assigned supplement within 30-minutes of mixing.
- Supplement compliance will continue to be encouraged by weekly phone calls by study personnel and compliance logs/supplement counts will occur at least twice per month.

Supplementation on Testing Days

On testing days, The BEETELITE™ solution (beet root) will be administered on-campus 20-45 minutes before subjects undergo the baseline, midpoint (following IMRT), and endpoint (4-6 weeks following midpoint) strength/endurance measures. Prior to testing, subjects will not have to refrain from standard oral care, using antibacterial mouth wash, or chewing gum 48 hours before testing sessions because the BEETELITE™ product does not rely on salivation/oral bacteria to convert dietary nitrate to nitrite (23). Previous studies have administered up to 500mL of beet root per day with nitrate concentrations of 5.5 mMol (24), 6.2mMol (7, 25), 5.2mMol (26), and 5.1mMol (27). Plasma nitrite (NO_2^-) levels in these aforementioned studies also increased following dietary nitrate supplementation.

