7.1 Adverse Event List(s) for Concentrated Beet Root

BEET ELITE™ is an oral concentrated beet root dietary supplement and not specifically FDA approved. Since BEET ELITE™ is not a drug, there is no Investigator Brochure. This supplement will be obtained from Neogenis® Labs, Inc., Austin, Texas. The BEET ELITE™ product is made from organic beet root crystals, natural flavors, malic acid, and stevia extract and is manufactured in a GMP certified facility. The concentration of the shot is equivalent to 6 beets in one shot.

Beet Root Toxicities:

Potential adverse effects of beet root are rare and include: stomach cramping/diarrhea, pink coloration of urine and stools, and allergic reactions. These side effects are consistent with events that may occur with normal beet consumption (as a food). There have been no reports of mucosal injury in the head and neck, or irritating effect on the oral mucosa.

Methemoglobinemia has been reported in infants who have consumed high levels of nitrate, but these findings have largely been discredited due to confounding cases of gastroenteritis and co-ingestion of sodium nitrite (from contaminated well water). Methemoglobinemia has not been documented in adults consuming nitrates at the level proposed in this trial. Given the oxalate content of beet root (28), caution should be taken for individuals with a history of nephrolithiasis or gall bladder dysfunction.

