8.1.2 Beet Root Juice (BEET ELITE™) Product Description

Product description: BEET ELITE™ is an oral concentrated beet root dietary supplement. One 10g packet contains both nitrate and nitrite. Typically, only about 5% of beet nitrates are metabolized to active intermediates taking at least 90 minutes. BEET ELITE™ is a revolutionary formula that includes a natural form of nitrite, thus bypassing the inefficient nitrate reduction process. BEET ELITE™ begins working in 15 minutes and has the Nitric Oxide content of 6 beets in one shot. The recommended dose is typically one shot per day. Product is available through Neogenis® Labs, inc., and is available online as a dietary supplement.

8.1.3 Solution preparation:

BEET ELITE™ products are individually packaged in 10g packets and must be mixed with 120ml of water and consumed within 30 minutes of mixing. Participants will be taught to prepare and self-administer their assigned study supplement and IDS will provide participants with the water and powder packet during the IMRT treatment period.

8.1.4 Route of administration:

BEET ELITE™ products will be self-administered throughout the entire study period via enteral

tube (PEG) or by mouth as a thin liquid (PO). Participants will be asked to take this product mixed with water (120ml) daily (M-F) without supervision. Participants will be instructed to administer BEET ELITE™ in the afternoon hours by mouth or by using their PEG tube in accordance with standard PEG feeding tube guidelines. Participants should flush their feeding tube with 30-50mL of water before and after supplementation. This supplement can be served cold or at room temperature within 30 minutes of mixing and may be tolerated best at room temperature if given enterally.

8.2 Labeling:

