11. MEASUREMENT OF EFFECT

11.1 Toxicity

For the purposes of this study, patients receiving beetroot supplement will be re-evaluated for toxicity as listed above and weekly during radiation as per institutional standard. All subjects receiving beetroot supplement will be evaluated for toxicity from the time of their first treatment with beet root to the end of study. Subjects will also be required to record each dose of beet root juice, including date and time, and subjective side effects (i.e. nausea, diarrhea, allergic reactions) noted after each dose. Subjects receiving only muscle strength testing will not be followed for toxicity as they receive standard of care and supportive medications as per routine. These subjects are not considered to be part of the interventional study but certainly serve as a baseline observational cohort.

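### Read alone, Section 6 resumes beetroot at an unchanged 10 g per dose after a grade 3 or 4 allergic reaction, unless a physician invokes the undefined criteria in 5.3

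*Combined protocol and SAP*

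**What the plan says.** Section 6 applies to adverse events at least possibly related to beetroot and refers staff to a short table. Grades 1 and 2 need no change. Grades 3 and 4 share one instruction: "Hold until recovery to grade 2 or less, then decrease to Monday-Wednesday-Friday dosing". The table has no row for permanent discontinuation. Beneath it stands: "Exceptions to this procedure include: any grade alopecia and grade 3 or 4 fatigue".

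Section 7.1 gives the potential effects of beetroot, described as rare, as "stomach cramping/diarrhea, pink coloration of urine and stools, and allergic reactions". Section 11.1 asks patients to record "subjective side effects (i.e. nausea, diarrhea, allergic reactions) noted after each dose".

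On the dose, Section 5.1.3 states: "Subjects will be given 10 grams of concentrated organic beetroot crystals". Supply is in pre-measured 10 g portions, five a week, and no smaller portion is described. Section 8.1.4 adds: "Participants will be asked to take this product mixed with water (120ml) daily (M-F) without supervision". On testing days the supplement "will be administered on-campus 20-45 minutes before subjects undergo the baseline" strength measures, and likewise before those at midpoint and endpoint (5.1.3).

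Section 5.3 begins "Subjects will be removed from study if one of the following occurs". Its list includes an unacceptable adverse event, and a change in condition that in the investigator's judgment makes the patient unacceptable for further treatment.

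**The concern.** Cutting the number of doses per week is a reasonable response to an effect that depends on cumulative exposure. It is the wrong response to a severe allergic reaction, where a single further exposure may do the harm. The protocol foresees the event, since it lists it and asks patients to log it, yet gives it the same step-down as everything else. The two named exceptions, alopecia and fatigue, are not on the 7.1 list of beetroot effects, whereas allergic reaction is.

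At stake is the safety of an individual patient who follows a written instruction, and the position of a physician who would have to go outside Section 6 to avoid it.

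**Working it through.** The plan states no figure on this point to reproduce. The check is a side-by-side reading with simple dose arithmetic.

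**1. Does the rule reach an allergic reaction?** Section 6 is limited by grade (3 or 4) and attribution (at least possibly related), not by type of event. Allergic reaction is a listed beetroot effect (7.1) and is not among the named exceptions. It is therefore covered.

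**2. What does the rule then direct?** Hold, then resume. The condition for resuming is grade 2 or less, so full resolution is not required.

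**3. What is the patient re-exposed to?**
- Amount per dose: 10 g before the event (5.1.3) and 10 g after, because Section 6 changes the schedule only. Reduction = (10 − 10)/10 = 0%.
- Amount per week before: 5 × 10 g = 50 g (Monday to Friday).
- Amount per week after: 3 × 10 g = 30 g (Monday, Wednesday, Friday).
- Weekly reduction = (50 − 30)/50 = 40%, all of it from frequency.

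**4. Is the first resumed dose supervised?** Staff supervise the initial self-administration (5.1.3), and testing-day doses are given on campus. Otherwise dosing is normally unsupervised (8.1.4), and nothing requires supervision of the first dose after a hold.

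**5. Does another section stop dosing?**
- Section 3.2 excludes calcium oxalate stones and malabsorption, but not known beet allergy.
- Section 5.2 has its own grade 3 or 4 diarrhea rule, with recovery to grade 1 or less. It has no counterpart for allergic reactions.
- Section 7.3.3 requires grade 4 events to be reported within 5 calendar days, unless the protocol lists them as exempt; 7.3.4 lists none. A report does not itself stop dosing.
- Section 5.3 can stop dosing, by removing the patient from the study. It does not define unacceptable, does not name allergy, and is not referred to in Section 6.

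**6. Does stopping beetroot change who is analysed?** Section 13.4.1 puts all beetroot patients in the safety analysis. Section 13.4.2 assesses all patients for treatment compliance, even with major protocol deviations, and its intent-to-treat set may leave out only those who took no study product. An eligible patient who reacted to beetroot has taken it, so stays in both sets. The per-protocol set differs: fewer than 3 supplements in any one week between baseline and midpoint excludes the patient (5.1.3). Monday-Wednesday-Friday dosing gives exactly 3, a margin of 0 doses; a permanent stop gives 0.

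**The case against.** A reader might infer that the protocol compels rechallenge after a severe allergic reaction. The documents do not support that. Section 5.3 is worded as mandatory, and a treating physician could readily call a grade 3 or 4 allergic reaction unacceptable. Section 6 says that its exceptions include the two it names, so the list is not stated to be closed. Section 5.2 shows that event-specific management can sit outside Section 6.

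There are other safeguards. Physicians assess toxicity and attribution weekly (5.2), supplement is dispensed weekly during radiotherapy (5.1.3), and the monitoring committee reviews all adverse events (4.4). The protocol calls beetroot effects rare and consistent with eating beets as food (7.1). Most clinicians would stop the product without being told.

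Much of this stands, and it keeps the point small. It does not remove it. No section adds allergic reactions to the exceptions. The route through 5.3 depends on a judgment that the protocol leaves undefined and that Section 6 does not mention. If every clinician would stop, the written rule should say so rather than rely on being set aside.

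Two further inferences should be resisted. Section 5.5 points to 5.4 for the removal criteria, which are in 5.3; that is a clerical slip and adds no weight to the safety point. Nor does the gap bias any estimate, since the safety and intent-to-treat sets are the same either way.

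**Conclusion.** The point holds as a gap in Section 6 read alone: for a foreseen event, its only instruction is to resume the same 10 g dose less often, possibly with a grade 2 reaction still present. Whether that happens depends on a physician invoking 5.3.

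The frequency of such reactions cannot be sized, because the documents give no rate and none is assumed here. What can be stated is the exposure of a patient who meets the rule: 0% reduction per dose and 40% per week. Up to 25 beetroot patients are covered. The conclusion assumes that the reaction is graded 3 or 4 under CTCAE v4.0 and attributed at least possibly to beetroot. It is a safety clarification worth making, of modest priority, with no bearing on sample size or the primary analysis.

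**What to change.** Make two linked changes.

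- **Section 6, added to the exceptions:** After any grade 3 or 4 allergic reaction at least possibly related to beetroot, beetroot (including testing-day doses) is permanently stopped without rechallenge.
- **Section 5.3:** Such an event ends beetroot only; the patient remains under assessment for treatment compliance and toxicity unless another criterion in 5.3 applies. Without this, the mandatory removal wording in 5.3 and the new exception could give conflicting instructions for the same patient.

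Separately, correct the pointer in 5.5 from 5.4 to 5.3.

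The cost is a few lines of text. An occasional misattributed event would end supplementation and slightly lower supplement completion. A patient stopped before midpoint leaves the per-protocol set: 1/25 = 4% of the beetroot cohort for each such patient. That is a cost of the fix, not the size of the problem, and it is not wholly new: removal under 5.3 also ends dosing, and a hold that leaves fewer than 3 doses in any week already excludes the patient. Later strength and nitrate/nitrite measures for that patient would be taken without the testing-day dose and should be flagged.

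The change leaves the grade 2 row alone, so dosing would still continue through an allergic reaction that never exceeds grade 2. Whether to tighten that, or to exclude known beet allergy at entry, is a clinical choice for the sponsor.
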